# 9.3 Patient Interviews (WP2c)

Those who consent to be followed up further after completing the consultation exit questionnaire will be contacted to arrange a telephone interview. We expect the interviews to take 15-30 minutes to complete.

Participants will be asked to provide verbal informed consent to take part in the interviews. Verbal informed consent will be audio recorded on an encrypted dictaphone and stored in accordance with the procedures outline in Section 10. Each of the statements on the consent form will be read out and patients will be asked to verbally indicate their agreement (or not) with each statement. This will be audio recorded. The researcher will then sign and date the written consent form and then provide the patient with a copy after the assessment. Each patient will have been provided with a participant information sheet and the activPAL instructions at least 24 hours prior to providing consent to participate.

Interviews will be semi-structured. Patients will be asked about their experience of their consultation with their GP using a height-adjustable workstation. They will be asked about the impact using the workstation had on the doctor-patient relationship and on their perception of the effectiveness of the consultation, particularly whether they believe the workstation impacted on this. They will also be asked if they felt their GP using the height-adjustable workstation had any effect on their own behaviour (time spent sitting, standing, moving and sleeping). Data from the interviews will be audio-recorded using an encrypted dictaphone and transcribed, summarised and coded by a Loughborough University approved commercial company (JC Porter, using the methods described and outlined in *Data Management* below).

# 10 Data Management

#### 10.1.1 Participant Contact Detail

GPs contact details will be recorded at baseline in the case report form. Patients will be asked to provide their contact details when consenting to the follow-up telephone interviews. Patients who complete the exit questionnaire but do not wish to take part in a follow-up interview do not need to provide their name or contact details. Any contact details obtained for GPs or patients will be retained and kept separate from their research data to enable anonymous research data collection. Any patient identifiable information recorded on the questionnaire will be logged and then removed. GPs and patients who consent for interviews will be given an identification number and their contact details will be stored on a separate study excel password protected study spreadsheet on the Loughborough University secure study server. Consent to participate in the study will be stored with raw data. Anonymous research data will be stored on the University's secure server for 10 years after the completion of the study.

# 10.1.2 Questionnaire and activPAL data

All questionnaire and activPAL data for GPs will not contain identifiable information but will be allocated an identification number which will be stored securely at Loughborough University. Patient exit questionnaires may contain identifiable information if they consent to provide contact information for the interviews. Anonymous research data will be stored on the University's secure server for 10 years after the completion.

# 10.1.3 Interviews

The interviews (both with GPs and patients) will be recorded using an encrypted dictaphone. All audio data collected will be transferred from the recording device to Loughborough University researcher's computer before being transferred onto the University's secure server as soon as connectivity is made. The original recording will then be deleted from the device.

Audio recordings will be transcribed by a commercial company who will have a confidentiality agreement in place with Loughborough University. The commercial company will remove and destroy all personally identifiable data from the transcripts and participants will be coded and referred to in study documents using a unique identification number. Anonymous research data will be stored on the University's secure server for 10 years after the completion. Consent forms will be stored for 10 years after the completion of the project in a locked filing cabinet at Loughborough in a separate office to anonymised data.

# 10.2 Data Analysis

Interviews will be recorded, transcribed and analysed. Overall, these will be compiled to help answer the research objectives stated previously.

Quantitative data, collected in the GP questionnaires, patient exit questionnaires and activPAL, will be analysed to help answer the research objectives stated previously. All quantitative data collected from patients will be collected at one time point. Quantitative data collected from GPs will be collected at two time points, baseline and during the intervention. This will allow us to analyse change in numerous variables for GPs, but not for patients. Analyses will mainly be descriptive as the study is not powered to determine effectives given the feasibility nature of this work.

# 11 Adverse events and serious adverse events

There is no reason to assume that this study will lead to an excess of adverse events. The intervention consists of GPs and their patients standing during their routine consultation, and GPs having conversations with their patients about physical activity and reducing sedentary behaviours. GPs promote physical activity within everyday life, which is not likely to create harm. Furthermore, the promotion of physical activity by health professionals is already part of standard care and has been demonstrated as being low risk for all citizens in England as per the NHS Making Every Contact Count Campaign (ref) without specific follow-up for adverse events. Therefore, no adverse events will be collected for this research. Given the low risk nature of the intervention, no formal evaluation of serious adverse events will be included either.

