# 5.2 Exclusion criteria

GPs may not enter the study if ANY of the following apply:

- Medical student who is not yet qualified as a GP and any other health care professional.
- Pre-existing condition that inhibits an individual's ability to stand or to be physically activity.

Patients may not enter the study if ANY of the following apply:

• Unable to communicate in English and unable to provide written informed consent.

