#### 12.2 Ethical Considerations

#### 12.2.1 Risks

Participation in the proposed research has very limited risks. Consenting to participate will require GPs to wear an activPAL accelerometer for ~16 days in total. There are minimal risks associated with wearing an activPAL for this length of time. It is possible to have a small amount of skin irritation caused by the waterproof dressing attaching the device to the thigh. To prevent this, GPs are encouraged to remove the device to clean the skin on a regular basis and can switch thighs if required. Other risks associated with other study related activities are in line with normal everyday risk and participants who agree to take part will be asked to provide written informed consent and will be informed of their right to withdraw from the study at any time. All data will be handled in accordance with the latest data protection legislation and anonymised for the purposes of data analysis and reporting. No sensitive data will be collected as part of the study.

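### Section 11 rules out collecting adverse events for reasons that concern promoting physical activity, not standing or the activPAL dressing, so common minor harms will not be counted

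*Protocol*

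**What the plan says.** Section 11 describes the exposure first: "The intervention consists of GPs and their patients standing during their routine consultation", together with conversations about activity and sitting. It then gives two reasons for expecting no excess of events. One is "GPs promote physical activity within everyday life, which is not likely to create harm". The other is that promotion by health professionals is already standard care and low risk, "as per the NHS Making Every Contact Count Campaign (ref) without specific follow-up for adverse events"; the reference there is an unfilled placeholder. From these it concludes "Therefore, no adverse events will be collected for this research", and for serious events "no formal evaluation of serious adverse events will be included either".

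Section 12.2.1 describes the monitor: "Consenting to participate will require GPs to wear an activPAL accelerometer for ~16 days in total". It names a possible event: "It is possible to have a small amount of skin irritation caused by the waterproof dressing attaching the device to the thigh". It adds preventive steps and treats the remaining study risks as those of everyday life.

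Section 4.1 makes feasibility and acceptability to GPs and patients the primary objective. Objective 9 in section 4.2 covers the acceptability of the measurement instruments, including the activPAL.

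**The concern.** Section 11 decides affirmatively not to collect events, so this is not a detail left for an analysis plan. The reasons do not reach two of the things participants undergo: GPs working partly on their feet for four weeks, and an adhesive dressing worn for about 16 days. The protocol itself regards ability to stand as relevant, since section 5.2 excludes GPs with a condition that inhibits the "ability to stand or to be physically activity".

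Whether GPs tolerate standing and the monitor is part of whether they find them acceptable. Without a structured item, the study cannot say how many of its GPs had discomfort or a skin reaction, or how many stopped using the desk or monitor because of it. If a larger trial followed, an absence of reports could be taken for an absence of events.

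**Working it through.** The protocol gives no event rate, power or precision figure to reproduce. The check is first textual, then a calculation of what the planned sample could show.

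**Step 1. Does the rationale cover each exposure?**

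| Exposure | Where described | Reason in section 11 for not collecting events |
|---|---|---|
| Conversations promoting activity | Section 11 | Yes: everyday practice and standard care, reference unfilled |
| Standing at work | Sections 7.1, 8.5, 11 | None specific to standing |
| activPAL and dressing, about 16 days | Sections 8.6.1, 12.2.1 | None |

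**Step 2. Would another planned source count these events?**

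- GP follow-up questionnaire (section 8.6.2): asks whether the desk was used and, if not, why; whether it made the GP self-conscious; whether it was obtrusive; and about effects on consultations. No listed item covers discomfort, fatigue, skin reaction or the activPAL.
- GP interviews (section 8.7): cover the GP's own mental and physical health, but are by invitation and semi-structured.
- Patient exit questionnaire (section 9.2): covers posture, preference, relationship and understanding, with space for comments. No listed item asks about feeling unwell or unsteady.
- Patient interviews (section 9.3): about 20 to 25 expected (section 5.3), on experience of the consultation.

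These give qualitative or indirect information. None gives a count of harms over a known denominator.

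**Step 3. What could a simple GP record show?**

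Inputs: n = 30 to 40 GPs (section 5.3). The true event rates p are my assumptions.

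One-sided 95% upper limit with zero events, 1 − 0.05^(1/n):
- n = 30: 1 − 0.05^(1/30) = 9.5%
- n = 40: 1 − 0.05^(1/40) = 7.2%

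Probability of at least one event, 1 − (1 − p)^n:

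| Assumed p | n = 30 | n = 40 |
|---|---|---|
| 1% | 26.0% | 33.1% |
| 5% | 78.5% | 87.1% |
| 10% | 95.8% | 98.5% |

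If 10% of GPs reported an event, the exact two-sided 95% interval would be 2.1% to 26.5% for 3 of 30 and 2.8% to 23.7% for 4 of 40.

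These figures assume that every GP completes follow-up. With 20% attrition (my assumption), n = 24 to 32 and the zero-event limits become 1 − 0.05^(1/24) = 11.7% and 1 − 0.05^(1/32) = 8.9%.

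**Step 4. Patients.** For the target of 200 to 300 exit questionnaires, the same formula gives 1.5% to 1.0%. This is not a bound on harm from patients standing. Section 9.2 has GPs offer the form only where appropriate and records that some patients sit, and patients are clustered within GPs, which the simple binomial ignores.

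**The case against.** The strongest defence is that this is a reasoned choice in a small, single-group feasibility study of an optional desk. Section 7.1 leaves standing to the GP and patient, and patients need not stand. Section 12.2.1 calls the device risk minimal, describes slight skin irritation with steps to limit it, and classes other study risks as everyday ones, which arguably includes standing. That stands as an argument for low risk and lowers the severity. It does not supply the missing count.

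Four stronger readings are tempting, and the documents do not support them.

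- **The intervention is prolonged standing.** The lay summary encourages standing in as many consultations as possible, but no duration is fixed and the desk alternates between positions.
- **The study cannot report tolerability at all.** The interviews, the question on why a desk was not used, and free comments will give some information. What is missing is a systematic count.
- **Sections 11 and 12.2.1 contradict each other.** Naming and mitigating a slight risk is compatible with not logging it. The gap is that the rationale does not address the named risk.
- **Patients lack a needed exclusion for inability to stand.** Patients are recruited on leaving the consultation (section 9.1), so such a criterion would apply after exposure. The reference to able-bodied adults in section 8.6.2 is questionnaire wording, not an eligibility rule.

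**Conclusion.** The concern holds in limited form. The decision to collect no adverse events is supported only for the promotion of physical activity. Harms from standing or the dressing will not be counted, and tolerability rests on voluntary interviews, free text and indirect items.

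A record from 30 to 40 GPs would probably show a minor event that is common, at 5% to 10%, and would bound it at 9.5% to 7.2% if none occurred. It would say little about events near 1%. These figures rest on assumed rates, independent GPs and full follow-up; attrition widens them.

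Severity is minor to moderate. No planned estimate is biased by the omission and the described risk is low, but an acceptability question is left without an easily obtained number.

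**What to change.** 1. Add yes/no items to the GP follow-up questionnaire completed at workstation removal: new or worse musculoskeletal discomfort; skin reaction to the dressing; and whether either led the GP to stop using the desk or the monitor.
2. Report counts with exact confidence intervals over the GPs who answered, giving the number who did not. State that rare harms cannot be excluded.
3. Reconcile section 11 with section 12.2.1 so that the rationale covers standing and the device, and fill in the missing reference. If no items are added, state that information on harms comes only from interviews and free text.
4. Any item on the patient exit form is optional. Report it only as a proportion among form completers who stood, because the form is handed out selectively and some patients sit.

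The cost is a slightly longer GP form and a rewritten paragraph. No extra visit is needed, since the questionnaire is already given. A reporting route that required judging relatedness would need staff time, and anonymous patient forms would limit follow-up, so it is not part of this recommendation.

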#### 12 Research Governance

The University has an Information Protection Unit that provides support and information to staff in ensuring they are fully compliant with all Information Governance requirements. All investigators are aware of and will work in line with the UK Policy Framework for Health and Social Care Research and have completed GCP training in line with NIHR requirements. A Favourable Ethical Opinion will be obtained from the Health Research Authority Research Ethics Service and Health Research Authority (HRA) Approval. No potential participants will be contacted until all ethical and R&D approvals are in place.

# 12.1 Data Management

All research data relating to WP2b will be anonymous unless participants wish to disclose their personal details. All personal data gathered will be detached from research data and will be stored separately at Loughborough University. Continued consent to store contact details for future research will be taken from participants prior to research activities. Loughborough University is the custodian of the data and therefore both electronic and paper-based data will be stored on the University's Secure Servers in line with the University's Privacy Statement. Loughborough University are the data controllers for the study and have completed a Data Protection Impact Assessment. The transcription company are data processors, are compliant with General Data Protection Regulations (GDPR) guidance and have a confidentiality agreement in place with Loughborough University.

#### 12.2 Ethical Considerations

#### 12.2.1 Risks

Participation in the proposed research has very limited risks. Consenting to participate will require GPs to wear an activPAL accelerometer for ~16 days in total. There are minimal risks associated with wearing an activPAL for this length of time. It is possible to have a small amount of skin irritation caused by the waterproof dressing attaching the device to the thigh. To prevent this, GPs are encouraged to remove the device to clean the skin on a regular basis and can switch thighs if required. Other risks associated with other study related activities are in line with normal everyday risk and participants who agree to take part will be asked to provide written informed consent and will be informed of their right to withdraw from the study at any time. All data will be handled in accordance with the latest data protection legislation and anonymised for the purposes of data analysis and reporting. No sensitive data will be collected as part of the study.

#### 12.2.2 Potential benefits

GPs may benefit in the short term from using a height-adjustable workstation at work, although this is not likely to provide benefits beyond the short term due to the limited time frame in which the workstation will be used. There are no expected benefits to patients taking part in this research, but it may encourage them to become more physically active and sit less during the day.

# 13 **Funding**

This research is funded via an NIHR Research Professorship award to [name] (Reference number: NIHR300026). As NIHR funded research this work is eligible for adoption on the NIHR Portfolio where the excess treatment costs will be funded via the Primary Care Research Network – West Midlands.

# 15 Appendix A

Example of height-adjustable workstation to be used in WP2a
